#### 3.2 Valve-related thromboembolism

Valve-related thromboembolism is defined as any thromboembolic stroke, thromboembolic transient ischemic attack (TIA), thromboembolic myocardial infarction, or arterial thromboembolism to another organ or limb, occurring after the immediate perioperative period and not associated with infection or intracardiac tumor. The independent CEC committee will determine whether a thromboembolism was related to the On-X valve based on clinical evaluation, surgery, and autopsy data. If the thromboembolism is determined to be of unknown origin after clinical evaluation, surgery, and/or autopsy, the thromboembolism will be conservatively considered to be related to the On-X valve.

#### 3.3 Major bleeding

Major bleeding is defined as any episode of internal or external bleeding that causes death, hospitalization, or permanent injury (e.g., vision loss) or necessitates transfusion, pericardiocentesis or reoperation. Bleeding will be adjudicated by the CEC Committee. Secondary definitions of bleeding, including Bleeding Academic Research Consortium (BARC) and International Society of Thrombosis and Hemostasis (ISTH) definitions of bleeding, will also be adjudicated.

#### 3.4 Quality of Life (EQ-5D-5L) Questionnaire

The survey is collected at Baseline, Month 1, Month 6, Month 12, and Month 24.

EQ-5D-5L questionnaire asks questions that are used to derive 5 subscales: mobility, self-care, usual activities, pain/discomfort, and anxiety/depression. Each question has 5 choices for health state ranging from best ("no problems") to worst. A Each subscale is created by summing up the answers to the questions affiliated with the subscale, ensuring that 1 is assigned to the answer indicating no problems and 5 is assigned to the answer indicating worst problem.

An index-based summary score is created as follows:

- a) Each subscale is multiplied by a constant obtained from table 2 of the US Valuation of EQ-5D-%L Health States Using an International Protocol (Simon et al., 2019)
- b) After subscales have been multiplied by the constant, the index is derived as follows: 1 – absolute value (sum of subscales multiplied by the constant in step a. Lower summary score represents better quality of life. If any items of those 5 items is missing, the summary score is missing.

The EQ VAS score is a separate question on the EQ-5D-5L that represents health status at the time the questionnaire was filled out (0 indicating worst health one could imagine through 100 indicating best health one can imagine).

Section 6.5 of this document describes the analysis for these measures.

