#### 1.1.4 Exploratory Objectives

- To compare apixaban with warfarin (INR target range 2.0 – 3.0) for health-related quality of life (EQ-5D-5L) in patients with an On-X mechanical heart valve implanted in the aortic position
- To compare apixaban with warfarin (INR target range 2.0 – 3.0) for the anticoagulation satisfaction (DASS) in patients with an On-X mechanical heart valve implanted in the aortic position

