## 6.5 Exploratory Analysis

The total DASS score as well as the 3 subscales (hassle, limitations, and positive impact will be analyzed as described below.

The EQ-5D-5L index, the subscales (mobility, self-care, usual activities, pain/discomfort, and anxiety/depression) as well as the EQ VAS score will be analyzed as described below. A repeated-measures mixed-effects model with Baseline score as a covariate will be run for each measure described above. The follow-up time-points responses (Month1, Month6, Month 12, and Month 24) will be included as outcome variables, and time as a fixed-effect variable.

Restricted maximum likelihood estimation will be used to model all available data from each subject without imputing missing values. An unstructured covariance matrix will be used, if the model doesn't converge, then a compound symmetry will be used.

Point estimates for each treatment group and treatment group mean differences (Apixaban - warfarin treatment) with 95% confidence intervals (CIs) will be generated for each time point. Additionally, the treatment effect will be averaged across all follow-up time points. The estimated treatment difference and 95% CIs will be obtained using the ESTIMATE Statement in SAS PROC MIXED. However, if the total missing value is greater than 10%, then descriptive statistics will be presented for the non-missing values by visits and overall.

“Total Missing” is derived as follows:

- Numerator: Number of participants missing measure of interest across visits
- Denominator: Number of participants expected to have the measure of interest across visits (# patients in population \* 5 visits). Denominator will not take into account when patients died, were lost to follow-up, or withdrew consent.

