### 7.1.5 Quality of Life and Satisfaction with Anticoagulation

Table 5.1	EQ-5D-5L Index Score Change Over Time by Treatment
Table 5.2	Duke Anticoagulation Satisfaction Scale Total Score Change Over Time by Treatment

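### SAP v1.4 section 3.4, as written, multiplies the 1-to-5 EQ-5D-5L score by the value-set constant and states a direction that its own formula contradicts (minor, exploratory index only)

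*Combined protocol and SAP*

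**What the plan says.** SAP v1.4 section 3.4 builds the index in three moves.

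- Dimension scores: "Each subscale is created by summing up the answers to the questions affiliated with the subscale". The coding rule attached to this reads "ensuring that 1 is assigned to the answer indicating no problems and 5 is assigned to the answer indicating worst problem". Each of the five subscales is therefore the raw 1-to-5 answer.
- Step a: "Each subscale is multiplied by a constant obtained from table 2" of the cited US valuation study. The constants are not listed, and the text does not say whether there is one per dimension or one per dimension and level.
- Step b: "the index is derived as follows: 1 – absolute value (sum of subscales multiplied by the constant in step a".

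The paragraph then adds: "Lower summary score represents better quality of life".

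The index serves an exploratory objective in section 1.1.4, a comparison of the arms "for health-related quality of life (EQ-5D-5L) in patients with an On-X mechanical heart valve implanted in the aortic position". Section 6.5 specifies: "A repeated-measures mixed-effects model with Baseline score as a covariate will be run for each measure described above". If total missing data exceed 10%, it falls back to descriptive statistics. The results go to Table 5.1 ("EQ-5D-5L Index Score Change Over Time by Treatment") and to the box plots of Figure 5. No other section of the protocol or of either SAP restates or corrects the scoring rule.

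**The concern.** A scoring rule in a SAP has to be programmable as written. This one multiplies a level code by a constant. It does not use the code to select the constant, and it does not subtract 1 from the code first. A programmer who follows it literally will either take something off for a patient who reports no problems, or count the constant for each higher level several times over. The sentence on direction adds a second difficulty, because it appears to run against the formula directly above it.

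At stake are the absolute index values by arm and visit, possibly the size of the arm differences, and the sign with which the apixaban minus warfarin difference is read.

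**Working it through.** The documents give no index value, range or example, so there is no figure to reproduce. The check evaluates the written formula.

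**Inputs.** Dimension score x_d from 1 to 5, five dimensions, and index = 1 − |Σ x_d·c_d|, all from SAP v1.4 section 3.4. The constants are assumptions, because the cited table is not in the documents. They are taken as non-zero (apart from level 1 in case B), of one sign, and equal across dimensions for simplicity.

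**Case A: one constant c per dimension.** A patient at level k on all five dimensions scores 1 − 5kc.

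| Assumed c | 11111 | 33333 | 55555 |
|---|---|---|---|
| 0.02 | 0.90 | 0.70 | 0.50 |
| 0.05 | 0.75 | 0.25 | −0.25 |
| 0.10 | 0.50 | −0.50 | −1.50 |

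The no-problems profile falls below the formula's starting value of 1 by 5c. Each step within a dimension costs the same c, whichever levels it joins. The formula can be rewritten as 1 − Σ c_d·x_d = (1 − Σ c_d) − Σ c_d·(x_d − 1). The term Σ c_d is the same for every patient at every visit. It therefore drops out of arm differences and changes over time, and the intercept absorbs it in a model with baseline as a covariate. It stays in the point estimates by arm, the descriptive statistics and the box plots.

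**Case B: a constant w_L for each level, with w_1 = 0, still multiplied by L.** With equal steps, w_L = (L − 1)s and w_5 = 4s. For w_5 = 0.20, s = 0.05 and w_3 = 0.10. All-level-3 then gives 1 − 5 × 3 × 0.10 = −0.50, against 1 − 5 × 0.10 = 0.50 if each constant is taken once.

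| Assumed w_5 | 11111 | 33333 as written | 33333 taken once | 55555 as written | 55555 taken once |
|---|---|---|---|---|---|
| 0.10 | 1.00 | 0.25 | 0.75 | −1.50 | 0.50 |
| 0.20 | 1.00 | −0.50 | 0.50 | −4.00 | 0.00 |
| 0.30 | 1.00 | −1.25 | 0.25 | −6.50 | −0.50 |

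Here differences are affected too. The charge at level L is L(L − 1)s, so moving from L to L + 1 costs (L + 1)Ls − L(L − 1)s = 2Ls instead of s. That is 2, 4, 6 and 8 times the single-charge step for L = 1 to 4.

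**Direction.** In case A, and in case B when the constants do not shrink with severity, the summed product grows as any answer worsens, so the index falls. Under the formula, higher is better. The SAP says lower is better. Section 6.5 estimates apixaban minus warfarin, so a positive difference favours apixaban by the formula but would be read as favouring warfarin by the sentence.

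**The case against.** The strongest reply is that the wording is shorthand. The SAP cites a published table, and an experienced programmer may look up the constant for the level answered and apply it once. No scoring program is in the documents, so this cannot be excluded, and that part stands. It does not rescue the text. The subscale is defined as the 1-to-5 score, section 6.5 analyses those same subscales as outcomes in their own right, and both steps a and b refer to multiplication. Reading the subscale as a 0/1 indicator contradicts that definition.

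Three further replies also stand. In case A the offset cancels in the treatment comparison, leaving shifted absolute values and the forced equal steps; whether equal steps depart from the cited values cannot be judged without the table. The SAP never says that 1 means full health, so the check speaks only of the formula's starting value. And the five dimension scores and the EQ VAS are analysed separately and do not pass through this formula.

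A reader might go further and infer that the reported index is not a valid EQ-5D utility. The documents do not support this: it depends on the form of the cited table and on how the rule was programmed, and neither is available. A reader might also infer that arm differences are inflated two- to five-fold. That range describes the charge at a single level in case B. It is not a range for arm differences, which depend on how patients are spread over levels. In case A, multiplying by the level code does not produce that inflation.

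**Conclusion.** The scoring rule is wrong as written; severity is minor. For non-zero constants of one sign, either the no-problems profile scores below the formula's starting value (by 5c: 0.10, 0.25 or 0.50 for assumed c = 0.02, 0.05 or 0.10) with forced equal steps, or level L is charged L times. This is algebra on the SAP's text and does not depend on the size of the constants; the numerical sizes do, and they are illustrations only.

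The contradiction on direction can be seen within the same paragraph, under the sign and ordering conditions given in the working. A wrongly computed index remains a risk, not an established fact. The effect is confined to the exploratory EQ-5D-5L index in section 6.5, Table 5.1 and Figure 5. The co-primary analyses, the major bleeding analysis, the significance level and the sample size are untouched.

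**What to change.** Replace steps a and b in section 3.4 with a lookup. For each dimension, take the table constant for the level answered (zero for level 1), and set the index to 1 minus the sum of the five constants, each taken once as a positive decrement, with no multiplication by the level code. Before adopting this wording, confirm it against the cited table, including whether its constants are level-specific and what sign they carry.

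Add two program checks: profile 11111 must return exactly 1, and profile 55555 must return the value that the table implies for the worst state. The first exposes the case A error and the second the case B error. In the same edit, change the direction statement to say that a higher index is better.

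The cost is one paragraph of SAP text and a check of the scoring macro, rerunning the index outputs if the macro followed the literal wording. No new data are needed.

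### SAP v1.4 section 3.4 says a lower EQ-5D-5L index is better, but its own formula makes a higher index better

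*Combined protocol and SAP*

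**What the plan says.** Section 1.1.4 of SAP v1.4 makes it an exploratory objective to compare the arms "for health-related quality of life (EQ-5D-5L) in patients with an On-X mechanical heart valve implanted in the aortic position". Section 3.4 defines the score in three steps:

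- **Coding.** Each of the five dimensions is scored "ensuring that 1 is assigned to the answer indicating no problems and 5 is assigned to the answer indicating worst problem".
- **Index.** Each dimension score is multiplied by a constant from a published US value table. The index is then 1 minus the "absolute value (sum of subscales multiplied by the constant in step a".
- **Direction.** The text then states "Lower summary score represents better quality of life".

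The same section defines the EQ VAS with "0 indicating worst health one could imagine through 100 indicating best health one can imagine", so higher is better on that scale.

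Section 6.5 reports "treatment group mean differences (Apixaban - warfarin treatment) with 95% confidence intervals" for the index at each time point and averaged over follow-up. It does not say which sign favours which arm. A fallback applies: "if the total missing value is greater than 10%, then descriptive statistics will be presented" in place of the model. In section 7.1.5, Table 5.1 is titled "EQ-5D-5L Index Score Change Over Time by Treatment". Neither that title nor the title of Figure 5 (box-plots over time, section 7.2) gives a direction.

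**The concern.** The formula subtracts a burden of problems from 1, so a healthier patient should score higher. The sentence after it says the opposite. It cannot be meant for the 1-to-5 dimension scores, where lower is indeed better: section 3.4 uses the term *summary score* for the index, both when it introduces the two-step derivation and when it gives the missing-item rule.

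This sentence is the only place where SAP v1.4 tells the reader how to interpret the index. If it is followed, a positive apixaban-minus-warfarin difference, which the formula makes favourable to apixaban, would be reported as favouring warfarin, and a negative one as favouring apixaban. The index would also seem to disagree with the EQ VAS from the same questionnaire whenever the two in fact agree. The slip is easy to miss because lower really is better on the neighbouring DASS total (section 3.5: 25 best, 175 worst).

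**Working it through.** **Inputs**

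- Dimension codes x₁ to x₅, each from 1 (no problems) to 5 (worst): SAP v1.4 section 3.4.
- Constants c₁ to c₅: from the cited value table, which the documents do not reproduce. Assumption: one constant per dimension, all of the same sign. Illustrative sizes: 0.01 to 0.10.
- Index = 1 − |c₁x₁ + … + c₅x₅|: section 3.4.

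The plan gives no numerical EQ-5D-5L figure to reproduce.

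**Step 1: direction for a single worsening.** With same-sign constants, |Σ cⱼxⱼ| = Σ |cⱼ|xⱼ, so index = 1 − Σ |cⱼ|xⱼ. Raising any xⱼ by one level changes the index by −|cⱼ|, which is always negative. Because of the absolute value, it does not matter whether the constants are all positive or all negative. There are 5⁵ = 3,125 response patterns and 5 × 4 × 5⁴ = 12,500 one-level worsenings; every one lowers the index.

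**Step 2: the two extremes, without the sign assumption.** Let S be the sum of the five constants. The best state (all 1s) scores 1 − |S| and the worst (all 5s) scores 1 − 5|S|. Best minus worst is 4|S|, which is positive for any constants that do not sum to zero. So even with mixed signs, the sentence is wrong for full health against the worst state.

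| Assumed constant per dimension | All 1s (best) | All 3s | All 5s (worst) |
|---|---|---|---|
| ±0.01 | 0.95 | 0.85 | 0.75 |
| ±0.03 | 0.85 | 0.55 | 0.25 |
| ±0.05 | 0.75 | 0.25 | −0.25 |
| ±0.10 | 0.50 | −0.50 | −1.50 |

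**Step 3: a pair of states**, with an assumed constant of 0.05.

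- Codes 1,1,1,2,1: sum 6, index 1 − 0.05 × 6 = 0.70.
- Codes 1,1,2,3,2: sum 9, index 1 − 0.05 × 9 = 0.55.

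The healthier state is higher by 0.15. The sentence would call it worse.

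**Step 4: does the reading of the constants matter?** If the table instead gives a separate decrement for each level, growing with severity, each worsening still enlarges the subtracted term and lowers the index. The direction is the same.

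**Step 5: a side point to check.** Read literally, the first step of the derivation multiplies the 1-to-5 code itself, so a patient with no problems loses Σ|cⱼ| and cannot score 1. With one constant per dimension this is the same shift for everyone. At 0.05 it is 5 × 0.05 = 0.25; without it the two states above score 0.95 and 0.80, still 0.15 apart, so the treatment difference does not change. That would not hold if level-specific constants were multiplied by the code.

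**The case against.** The strongest reply is that this is a wording slip in an unproofed paragraph. The formula, the coding, the model and the contrast are unaffected. The score is exploratory, carries no success criterion, and is not used in the co-primary or major bleeding analyses. An analyst who reads the formula printed just before the sentence may well notice the mistake. All of that is true, and it limits the importance of the point. It does not remove the contradiction: a pre-specified plan should not depend on the reader overruling its only stated rule of interpretation.

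A second reply is that the model-based difference may never be reported. Section 6.3.1's trial was, by section 6.1.3, stopped early, and the missing-data threshold in section 6.5 uses all patients times five visits as denominator, with no allowance for death, loss to follow-up or withdrawal. Month 24 is one visit in five, or 20% of that denominator, so if more than half of patients lack it the 10% threshold is passed even with all other visits complete. The documents do not say how many patients reached Month 24, so this is possible but not established. If it happens, arm-level summaries and box-plots replace the contrast, and they need the correct direction just as much.

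A third reply concerns the side point on how the constants are applied. The documents never say that full health must score 1, and the table is not available. That objection stands to this extent: the matter is something to check, not an error shown.

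**Conclusion.** The concern holds. Under the formula in section 3.4 a higher EQ-5D-5L index is better, and the sentence on direction is reversed. The numerical effect is nil: the estimate and its confidence interval change by 0. The interpretive effect is complete for this one score, since every index result would be attributed to the wrong arm by a reader who follows the sentence. The stated directions of the five dimension scores, the EQ VAS and the DASS total are consistent and unaffected.

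The conclusion for every single-level worsening assumes that the constants share a sign. The ordering of the best and worst states needs only that, with one constant per dimension, they do not sum to zero. The correction should be made, but nothing in the trial's primary, secondary or safety conclusions depends on it.

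**What to change.** - In SAP v1.4 section 3.4, change *Lower* to *Higher* in the sentence on the direction of the summary score.
- In section 6.5, state that a positive apixaban-minus-warfarin difference in the index favours apixaban.
- Add a footnote giving the direction to Table 5.1 and Figure 5, so that it also covers the descriptive fallback.
- Check the first step of the index derivation against the cited value table, and state whether there is one constant per dimension or one per level, how it is applied, and what applies to an answer of no problems.

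The cost is one word in 3.4, one sentence in 6.5, two footnotes and a look-up in the cited table, with a clarifying line if the look-up calls for one. Correcting the direction requires no change to data collection or to the model.

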### 3.5 Duke Anticoagulation Satisfaction Scale (DASS)

The survey is collected at Baseline, Month 1, Month 6, Month 12, and Month 24.

Duke Anticoagulation Satisfaction Scale (DASS) (Samsa et al., 2004) is a 25-items questionnaires to measure the positive and negative impact of anticoagulation, and each item has 7 choices ranging from “not at all” to “very much”. The 25-items are utilized to create 3subscles: hassle, limitation, and positive impact.

Subscales are created by summing answers to the questions below:

Hassle: Answers 1 =not at all through 7 = very much

- How much of a hassle (inconvenience) are the daily tasks of anti-clot treatment
- How much of a hassle (inconvenience) are the occasional tasks of anti-clot treatment? (
- How complicated do you find your anti-clot treatment to be?
- How time-consuming do you find your anti-clot treatment to be?
- How frustrating do you find your anti-clot treatment to be?
- How painful do you find your anti-clot treatment to be?
- Overall, how much of a burden do you find your anti-clot treatment to be?
- Overall, how much has anti-clot treatment had a negative impact on your life?
- Compared with other treatments you have had, how difficult is your anti-clot treatment to manage?

Limitations: Answers 1 =not at all through 7 = very much

- How much does the possibility of bleeding or bruising limit you from taking part in physical activities (for example, housework, gardening, dancing, sports, or anything else you would usually do)?
- How much does the possibility of bleeding or bruising limit you from traveling?
- How much does the possibility of bleeding or bruising limit you from getting the medical care you need (for example, visiting a dentist, chiropractor, or doctor of your choice)?
- How much does the possibility of bleeding or bruising limit your ability to work for pay?
- Overall, how much does the possibility of bleeding or bruising affect your daily life?
- Being on anti-clot treatment may mean changing some of your other habits as well.
- How much does anti-clot treatment limit your choice of food (diet)? (
- How much does anti-clot treatment limit the alcoholic beverages you might wish to drink
- How much does anti-clot treatment limit the over-the-counter medications (for example, aspirin, ibuprofen, vitamins) you might wish to take?
- How much do you worry about bleeding and bruising? QSTESTCD = “DASS0120”)

Positive Impact: Answers 7 =not at all through 1 = very much

- Overall, how confident are you about handling your anti-clot treatment
- How well do you feel that you understand the medical reason for your anti-clot treatment?
- How much do you feel reassured because of your anti-clot treatment?
- Overall, how much has anti-clot treatment had a positive impact on your life?
- Overall, how satisfied are you with your anti-clot treatment?
- How likely would you be to recommend this form of anti-clot treatment to someone else with your disease or medical condition?

Total score of DASS is the sum of the subscale scores. The score range is 175 (worst) and 25 (best), and if any item of those 25 items is missing, the total score is missing. Higher DASS total score represents higher negative impact (less satisfaction) of anticoagulation. The DASS was validated with 3 subscales: (1) limitations to daily activities, (2) hassles of anticoagulation treatment, and (3) positive psychological impact of anticoagulation.

Section 6.5 of this document describes the analysis for these measures.

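### One blank item among 25 makes the DASS total missing; under simple assumptions, a per-item skip rate above 0.42% moves the total-score comparison to descriptive statistics

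*Combined protocol and SAP*

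**What the plan says.** SAP v1.4 section 3.5 describes the DASS as a scale that "is a 25-items questionnaires to measure the positive and negative impact of anticoagulation". Each item is scored 1 to 7, with 1 always the favourable end. Three subscales (hassle, limitations, positive impact) are formed by summing, and the total is their sum, with a range of 25 to 175. On incomplete forms it says only that "if any item of those 25 items is missing, the total score is missing". It gives no missing-item rule for the subscales, no prorating rule and no code for an item that does not apply.

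Section 6.5 names as measures "The total DASS score as well as the 3 subscales", and adds: "A repeated-measures mixed-effects model with Baseline score as a covariate will be run for each measure described above". Missing values are not imputed. The switch then reads: "if the total missing value is greater than 10%, then descriptive statistics will be presented for the non-missing values by visits and overall". Its numerator is "Number of participants missing measure of interest across visits". Its denominator is the number of patients times five visits, with no reduction for death, loss to follow-up or withdrawal.

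Comparing satisfaction between the drugs is an exploratory objective (section 1.1.4). The only DASS table listed in section 7.1.5 is Table 5.2, for the total score. Section 6.1.3 records that the trial was stopped early.

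**The concern.** Taken together, the two rules can discard a form with 24 of 25 answers and then count it towards the limit at which the total-score comparison is given up. Some listed questions may not apply to everyone. One asks "How much does the possibility of bleeding or bruising limit your ability to work for pay", and another compares this treatment with others the patient has had. Blanks may therefore occur even among careful respondents.

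Two things are at stake. The first is the estimated treatment difference in the DASS total, the one DASS result with a listed table. The second arises even below the limit: the baseline score is a covariate and nothing is imputed, so a baseline form with one blank item has no total. That would ordinarily remove the patient's follow-up totals from the model as well.

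**Working it through.** **Inputs from SAP v1.4.** Items k = 25 and any-item rule (3.5); switch above 10%, denominator patients × 5 (6.5); loss hazard 0.026 per year (6.1.8). **Assumed, not in the documents:** the per-item skip rate p, how far skips cluster, and the share of absent forms.

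**1. The SAP's own figure.** 25 × 1 = 25 and 25 × 7 = 175, which matches the stated range. The arithmetic therefore uses 25 items. Section 3.5 lists 25 bullets (9 + 10 + 6), but one limitations bullet is a lead-in sentence rather than a question. That leaves 24 answerable questions (9 + 9 + 6), whose range would be 24 to 168.

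**2. Base case.** With independent skips, every form returned and counting per participant-visit, the share of totals missing is 1 − (1 − p)^k, and the limiting rate is p = 1 − 0.90^(1/k).
- k = 25: p = 1 − 0.90^(1/25) = 0.42%. At p = 0.42% the share missing is 9.99%; at 0.44% it is 10.44%.
- k = 24: p = 1 − 0.90^(1/24) = 0.44%.

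**3. Changing one assumption at a time (k = 25).** For clustering, a beta-binomial model with mean p and within-form correlation ρ was used. For a share m of absent forms, p = 1 − (0.90/(1 − m))^(1/25).

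| Assumption | Limiting skip rate | Missing at p = 0.44% |
|---|---|---|
| Base case | 0.42% | 10.4% |
| Clustered, ρ = 0.05 | 0.65% | 6.9% |
| Clustered, ρ = 0.20 | 1.25% | 3.6% |
| m = 1.8% | 0.35% | 12.1% |
| m = 5% | 0.22% | 14.9% |
| m = 10% | 0 | 19.4% |

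The 1.8% is the mean of 1 − exp(−0.026t) over t = 0, 1/12, 0.5, 1 and 2 years.

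If the numerator counts each participant with any missing total once, over patients × 5, the limit is reached when 1 − (1 − p)^125 = 0.5. That gives p = 1 − 0.5^(1/125) = 0.55%, and 0.44% would not pass.

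**4. Subscales at p = 0.44%, if a blank makes the subscale missing.**
- 6 items: 1 − 0.9956^6 = 2.6%
- 9 items: 1 − 0.9956^9 = 3.9%
- 10 items: 1 − 0.9956^10 = 4.3%

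Their limiting rates are 1.74%, 1.16% and 1.05%.

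**5. Baseline.** Under independence, the share of patients with no baseline total follows the same formula. At p = 0.2%, well under the limit, it is 1 − 0.998^25 = 4.9%.

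**6. Absent Month 24 forms.** If a share f of patients has no Month 24 form, that alone makes f/5 of the denominator missing: 5%, 10% and 15% for f = 25%, 50% and 75% (assumed shares). Above f = 50% the limit is passed whatever the item rule.

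**The case against.** The strongest reply is that little is lost. Section 6.5 models each measure separately, and the any-item rule is written for the total only, so the three subscales would still yield treatment differences with confidence intervals. Section 3.5 itself names them as the validated structure. This stands. A reader might infer that the whole DASS comparison is abandoned; the documents do not support that.

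A reader might also infer that blanks are certain and will concentrate in retired or older patients. The documents give no skip rate, retirement share or mode of collection. Every item offers a not-at-all answer, which someone who does not work could choose for the work item. An electronic form might not accept blanks. So blanks may occur, and no more can be said. Clustering, where present, raises the limiting rate rather than lowering it.

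The reply also notes that the early stop may pass the limit whatever the item rule. This stands as a limit on the remedy. It does not justify discarding nearly complete forms, because absent forms leave less of the 10% allowance for item blanks.

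Finally, the cited scoring paper is not available here, and it may itself require complete forms. That is a reason to check the remedy against it.

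**Conclusion.** The point holds for the DASS total only. With 25 items, independent skips, every form returned and missingness counted per participant-visit, a skip rate above 0.42% per item moves the total to descriptive reporting. The figure is 0.44% for the 24 answerable questions, about 0.65% to 1.25% with clustered skips, 0.55% if participants rather than participant-visits are counted, and 0.22% with 5% of forms absent. All of these rest on assumed skip behaviour.

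The subscale comparisons survive at such rates, although only the total has a listed table. The baseline loss applies below the limit too. The measure is exploratory and has no bearing on the primary efficacy or safety conclusions, so this is a minor improvement.

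**What to change.** In section 3.5:
- If at least half of a subscale's items are answered, set the subscale to the mean of the answered items times its number of items.
- Compute the total from the three subscales, and set it to missing only if a subscale has fewer than half its items answered.
- State that a blank is never summed as 0, which would be better than the best permitted answer of 1.

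In section 6.5, count missingness after this rule has been applied.

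Check the rule against the scale's published scoring, including whether limitations has 9 or 10 scored items, since prorating needs that number. Show the total from fully completed forms as a sensitivity check.

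The cost is a few sentences and a few lines of code. The downside is the assumption that a skipped item resembles the patient's other answers in that subscale. The change does not address Month 24 forms absent because of the early stop, which still count against the fixed five-visit denominator.
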